#### 6.4.2 Rationale for Initial Dose and Schedule

Based on the ICH S9 Guidance (**27**), an acceptable clinical starting dose for an oncology drug is 1/10 the severely toxic dose in 10% of the animals (STD10) in rats, or 1/6 the highest nonseverely toxic dose (HNSTD) in dogs. The NOAEL and HNSTD are considered approximate in these studies.

The non-clinical pharmacology, ADME, safety pharmacology and toxicology of ASN002 have been comprehensively evaluated. For systemic toxicity of ASN002, the NOAEL in the 28-day rat and dog toxicity studies were determined to be 20 mg/kg/day and 15 mg/kg/day, respectively. Based on the recommended body surface area conversion method, the rat and dog NOAEL equate to human equivalent doses of 3 mg/kg and 8 mg/kg, respectively. The proposed starting dose of 20 mg per day (dosed as 10 mg bid) is approximately 1/10 of the human equivalent dose (3 mg/kg) based on the NOAEL in the most sensitive species, i.e., rat, and lower than ICH S9 recommended 1/6 of the highest non-severely toxic dose. Asana BioSciences believes that, considering the intended patient population, the 10-mg bid dose represents a safe starting dose for human exposure.

Preliminary pharmacokinetic analysis of data from cohorts 1-6, and 4a- suggest a half-life at least 12-14 hours. Therefore, once daily dosing of ASN002 are being evaluated in parallel cohorts. Since no DLTs have been identified at the 75 mg BID cohort (150 mg total daily dose) and escalation has continued at 100 mg BID, the first QD regimen was 80 mg QD. Additional doses that are being evaluated include 120 mg QD. Patients will be accrued into these cohorts after safety assessment of the previous cohort during the DLT phase is completed, similar to that for the BID regimen. Since co-administration with a low-fat meal increased ASN002 AUC by about 80% compared to administration under fasted conditions, future cohorts may evaluate safety and tolerability of ASN002 when administered immediately after a light meal. The first dose level at which this evaluation will occur will not be greater than 75% of the highest dose administered under fasted conditions.

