---

**Investigational product, dosage and mode of administration:** ASN002 administered orally. Planned doses are 10, 20, 30, 40, 50, 75, and 100 mg q12h. Cohorts of subjects have been added to explore q24 h dosing, at 80 mg and 120 mg once daily. The initial qd dose will not exceed the total daily dose of the highest well tolerated bid dose. The initial dose taken with food will not exceed 75% of the highest tolerated dose. ASN002 is available in 5-mg, 20-mg, and 50-mg strength tablets.

**Duration of study:** Parts A and B will include a screening period (up to 28 days) and a treatment period up to 12 months. A subject with no DLTs may have the opportunity to continue treatment at the discretion of the investigator and sponsor. If the subject is not a candidate for, or chooses not to participate in additional treatment, an end-of-study visit will take place followed by a 4-week post-treatment period.

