#### 6.4.5 Rationale for the Evaluation of ASN002 with Food

Co-administration of ASN002 with a standardized low fat meal increased systemic exposure by about 80% in healthy subjects in a previous study. Future cohorts may evaluate safety and tolerability when ASN002 is administered immediately after a meal. The starting dose level at which the effect of a meal on safety, tolerability and pharmacokinetics will be evaluated will be

at least one dose lower than the highest dose evaluated when ASN002 was administered under fasted conditions

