## **8 INVESTIGATIONAL PLAN**

### **8.1 Study Design**

This study will be performed at approximately 3 to 15 study centers located in the United States and Latin America.

The study is an open-label, non-randomized, uncontrolled, multicenter, dose escalation, cohort expansion and extension study with single and multiple-dose PK in subjects with relapsed/refractory lymphomas, MF, CLL, and advanced/metastatic solid tumors for which no standard therapy exists. The study will be conducted in 2 parts:

- Part A: Evaluation of the safety and tolerability of escalating multiple doses of ASN002;
- Part B: Cohort expansion of 6 identified disease-specific cohorts (DLBCL, MCL, FL, PTCL, MF and CLL) from Part A to further evaluate the safety, tolerability and antitumor activity of multiple doses of ASN002.

Parts A will be a “3+3” dose escalation scheme beginning with dose level 1 at a dose of 10 mg every 12 hours. Subjects will receive a single dose of ASN002 on Day 1, followed by every 12 or 24 hours, as assigned, dosing beginning on Day 3. The dose of ASN002 will be escalated to identify DLTs, and the MTD. If an MTD is not identified by the last scheduled cohort, dose escalation will continue in less than or equal to 50% increments until the MTD is identified. If supported by the PK profile, transition to once daily dosing may be considered. The starting dose of the once daily (qd) dosing cohorts will not exceed the total daily dose of the highest twice daily dose that is considered safe and well tolerated. Daily dosing cohorts may include doses beginning at 60 mg QD. Additional dose escalation may be performed for the qd dose cohorts, if the MTD is not identified by the 100 mg qd dose.

[figure not shown]

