## 8.3 Selection of Doses

### 8.3.1 Part A (Dose Escalation)

Dose escalation will commence with dose level 1 (10 mg every 12 hours). Subsequent planned dose levels in Part A include: 20, 30, 40, 50, 75 and 100 mg administered every 12 hours or, 80, 120, and 150 mg every 24 hours. These planned dose levels may be modified based on data obtained throughout the course of study conduct. If an MTD is not identified after completion of the highest scheduled dosing cohort (either bid or qd) dose escalation may continue in

increments of  $\leq 50\%$  until the MTD is identified. The doses for twice daily and the single daily doses are found in **Table 6**.

The PK of ASN002 may be evaluated when administered with food. Up to 6 subjects per dose cohort may receive ASN002 after consuming a light meal. Subjects receiving ASN002 with food will receive no more than 75% of the highest dose that is deemed safe and well tolerated.

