**Table 6: Twice Daily and Once Daily Dosing Cohorts**

Twice Daily Dose Cohorts		Single Daily Dose Cohorts	
1	10 mg	N/A	
2	20 mg	N/A	
3	30 mg	N/A	
4	40 mg	4a a	80 mg
5 a	50 mg	5a a	120 mg
6 a	75 mg	6a a	150 mg
7 a	100 mg		

a Cohorts may be administered ASN002 with and/or without food.  
Dose escalation may continue in increments of  $\leq 50\%$  until the MTD is identified

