### 15.1 Determination of Sample Size

Part A: A traditional 3+3 design will be used. Including the 40 subjects currently enrolled in dose cohorts ranging from 10 – 100 mg BID and 80 and 120 mg QD, up to an additional 4 cohorts will be tested under fed conditions. It is anticipated that a total of 64 subjects may be enrolled in Part A. No randomization will be performed for Part A.

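### The limit on the dose given with food is tied to the highest fasted dose given in 6.4.2 and 6.4.5 but to the highest tolerated dose in the synopsis and 8.3.1, and its scope also differs

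*Protocol*

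**What the plan says.** Four places in the protocol limit the dose given with food.

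- **6.4.2:** the first fed level "will not be greater than 75% of the highest dose administered under fasted conditions".
- **6.4.5:** the starting fed level is to be "at least one dose lower than the highest dose evaluated when ASN002 was administered under fasted conditions".
- **Synopsis, investigational product entry:** "The initial dose taken with food will not exceed 75% of the highest tolerated dose".
- **8.3.1:** "Subjects receiving ASN002 with food will receive no more than 75% of the highest dose that is deemed safe and well tolerated".

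The first three cover only the first fed level. The fourth covers every subject dosed with food.

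Table 6, within 8.3.1, marks six cohorts (50, 75 and 100 mg BID; 80, 120 and 150 mg QD) with the footnote "Cohorts may be administered ASN002 with and/or without food". The footnote does not mention a cap. Section 15.1 plans that "up to an additional 4 cohorts will be tested under fed conditions".

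On doses already given, 15.1 describes 40 subjects "currently enrolled in dose cohorts ranging from 10 – 100 mg BID and 80 and 120 mg QD". Section 6.4.3 cites a pneumonia DLT in an NHL patient at 100 mg BID among the reasons for recommending 75 mg BID in hematologic malignancies. Sections 6.4.2 and 6.4.5 give the food effect as an increase in exposure of about 80%.

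No text ranks these limits. The one precedence clause (Protocol section 15) puts the SAP above the protocol, and the SAP contains no fed-dose limit.

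**The concern.** In a dose escalation, the highest dose given and the highest dose tolerated can differ, because escalation may stop on a dose that was given but not tolerated. A ceiling for a setting that raises exposure should rest on the tolerated dose. Two of the four statements rest on the dose given.

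The difference matters now. 100 mg BID has been given with one DLT cited, and the documents do not state whether the committee cleared it. Part A admits lymphoma patients. According to 6.4.4, the DLT at 100 mg BID and the pneumonitis at 120 mg QD were seen only in NHL patients. Section 6.3 reports infections in 1 of 10 patients at 60 mg daily or less and in 7 of 17 at 80 mg daily or more. A Part A subject with a DLT in Cycle 1 is discontinued rather than given a lower dose (8.3.3). A fed cohort opened on the rationale wording could therefore start above the level that 8.3.1 intends.

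**Working it through.** The documents give no fed dose in mg, so there is no figure of theirs to reproduce.

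**Inputs**
- Highest fasted BID dose given: 100 mg (15.1).
- Planned BID levels: 10, 20, 30, 40, 50, 75, 100 mg; planned QD levels: 80, 120, 150 mg (8.3.1, Table 6).
- Tablets: 5, 20, 50 mg (8.4). Planned levels may be modified (8.3.1), and the committee may choose an intermediate level (8.5.1).
- Food effect: factor 1.8 (6.4.2, 6.4.5), from a single-dose study in healthy subjects.
- Assumptions: exposure is proportional to dose, and the food effect carries over to patients.

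**Fed BID ceiling**

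| Rule | Reference dose | Ceiling | Highest usable level |
|---|---|---|---|
| 6.4.2 | 100 mg BID, given | 0.75 × 100 = 75 mg | 75 mg BID |
| 6.4.5 | 100 mg BID, evaluated | one level below 100 mg | 75 mg BID |
| Synopsis, 8.3.1 | 75 mg BID, if that is the tolerated dose | 0.75 × 75 = 56.25 mg | 50 mg BID planned; 55 mg (50 + 5) intermediate |
| Synopsis, 8.3.1 | 100 mg BID, if cleared | 0.75 × 100 = 75 mg | 75 mg BID |

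**Fasted-equivalent exposure (fed dose × 1.8)**
- 75 mg fed: 75 × 1.8 = 135 mg BID, which is 135/100 = 1.35 times the highest BID dose given.
- 55 mg fed: 55 × 1.8 = 99 mg BID.
- 50 mg fed: 50 × 1.8 = 90 mg BID.
- Ratio between the readings: 135/99 = 1.36 to 135/90 = 1.5.
- Break-even: 75 mg fed exceeds 100 mg fasted once the food effect is above 100/75 = 1.33, that is +33%.

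**Table 6 footnote against the 8.3.1 cap.** The cleared fasted dose needed is the fed dose divided by 0.75.

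| Footnoted fed cohort | Needed, same regimen | Above highest planned level of that regimen? | Fed total per day | Above 150 mg/day? |
|---|---|---|---|---|
| 50 mg BID | 66.7 mg BID | no | 100 mg | no |
| 75 mg BID | 100 mg BID | no | 150 mg | no |
| 100 mg BID | 133.3 mg BID | yes | 200 mg | yes |
| 80 mg QD | 106.7 mg QD | no | 80 mg | no |
| 120 mg QD | 160 mg QD | yes | 120 mg | no |
| 150 mg QD | 200 mg QD | yes | 150 mg | no |

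The last column uses 75% of the largest planned fasted daily total: 0.75 × 200 = 150 mg (100 mg BID is 200 mg per day). The footnoted cohorts that need a cleared dose above the planned levels number three of six on a same-regimen reading and one of six on a total-daily-dose reading. The higher doses are not unreachable, because 8.1 says "dose escalation will continue in less than or equal to 50% increments until the MTD is identified" if the last scheduled cohort does not identify an MTD. The steps needed are 133.3/100 = 1.33, 160/150 = 1.07 and 200/150 = 1.33.

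**The case against.** The strongest reply is that the four statements do not compete. Each is an upper limit, all can be met at once, and the strictest binds without a precedence clause. The looser wording sits in sections titled as rationale, while the dose-setting section and the synopsis agree on the tolerated-dose reference. This stands. A reader might infer that the protocol permits 75 mg BID with food outright. Taken as a whole it does not: 8.3.1 bars that dose unless 100 mg BID has been cleared.

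Second, the gap between reference doses depends on a fact the documents leave open. One cited DLT does not meet the rule of at least 2 of 6 in 8.5.2, Table 7 lists 100 mg BID as the level above the recommended dose, and 6.4.4 continues dose finding in solid tumors. Against that, 8.1 describes Part B as expanding the MTD cohort, and 8.3.2 starts it at 75 mg BID. It would go too far to infer that 100 mg BID was judged intolerable. If it was cleared, the reference doses agree and only the question of scope is left.

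Third, the Table 6 footnote is permissive and sits inside 8.3.1, so it need not override the cap. The protocol also compares QD with BID on total daily dose when it sets the first QD dose, which favors the one-of-six count. Both points are fair, but the cap itself does not state its basis.

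Fourth, harm is limited. Fed cohorts stay within Part A's 3+3 scheme with committee review, and a 1.35-fold step lies inside the 50% increment allowed for escalation. This lowers the stakes without settling which reference dose applies.

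**Conclusion.** The inconsistency is real and should be corrected, although it does not amount to an unsafe dosing rule in the protocol as a whole. Two statements tie the first fed level to a dose that was given but may not have been tolerated. Read alone, they allow 75 mg BID fed. With 75 mg BID as the tolerated dose, the synopsis and 8.3.1 allow 56.25 mg at most, in practice 50 or 55 mg BID. The difference in predicted exposure is 1.36- to 1.5-fold, and it vanishes if 100 mg BID has been cleared.

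The exposure figures rest on dose proportionality and on the healthy-subject food effect holding in patients. The count of affected footnoted cohorts, three or one of six, depends on the unstated basis of the cap. Whether the cap covers fed levels after the first is stated only in 8.3.1 and needs confirming whatever the status of 100 mg BID. The Part B sample size and error rates are not affected.

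**What to change.** 1. In 6.4.2 and 6.4.5, replace the references to the dose administered and the dose evaluated with the highest fasted dose that the safety review committee has cleared as safe and well tolerated. This matches the synopsis and 8.3.1.
2. State that the 8.3.1 cap applies to all fed cohorts, and whether it is calculated within the same regimen or on total daily dose.
3. Make the Table 6 footnote explicitly subject to that cap.

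This is a text amendment to make before a fed cohort opens. Its possible cost is a lower fed starting dose and one more escalation step. A lower, exposure-neutral cap is not needed.

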#### 6.4.3 Rationale for Recommended Part B Dose

The safety review committee met on May 18, 2017 to review and discuss clinical experience and key safety data. It was agreed that the recommended dose for Part B of the study will be 75 mg BID in patients with hematologic malignancies and that enrollment in Part B can proceed. The selection of the recommended dose was supported by the observation of SAE / DLT (Pneumonia) of a NHL patient at a dose of 100 mg BID, the observed cumulative hematologic toxicity in patients enrolled at a dose of 120mg QD and the SAE (Pneumonitis) observed in a NHL patient at Cycle 2 considered possibly related to ASN002.

At the recommended dose of 75 mg BID good systemic exposure and inhibition of serum biomarkers of inflammation can be observed. In NHL patients, treatment duration for more than 6 months without dose limiting toxicities and evidence of clinical activity is observed.

#### 6.4.4 Rationale for Additional Dose Finding in Advanced Solid Tumors

The SRC also noted that the dose limiting toxicity (Pneumonia) at 100 mg BID and the Cycle 2 SAE (Pneumonitis) at 120 mg QD were reported only in NHL patients, while patients with solid malignancies enrolled at 120mg QD were dosed up to 4 cycles without need for dose reduction.

The SRC agreed to continue dose finding for patients with solid malignancies to further characterize safety, PK and PD in this study population.

#### 6.4.5 Rationale for the Evaluation of ASN002 with Food

Co-administration of ASN002 with a standardized low fat meal increased systemic exposure by about 80% in healthy subjects in a previous study. Future cohorts may evaluate safety and tolerability when ASN002 is administered immediately after a meal. The starting dose level at which the effect of a meal on safety, tolerability and pharmacokinetics will be evaluated will be

at least one dose lower than the highest dose evaluated when ASN002 was administered under fasted conditions

## **7 OBJECTIVES**

### **7.1 Primary Objectives**

Part A:

- To evaluate the safety and tolerability of ASN002 including dose-limiting toxicities (DLTs) and to determine the maximum tolerated dose (MTD).

Part B:

- To evaluate the safety, tolerability, and preliminary efficacy of ASN002 in subjects with relapsed/refractory diffuse large B-cell lymphoma (DLBCL), follicular lymphoma (FL), mantle cell lymphoma (MCL), peripheral T-cell lymphoma (PTCL), myelofibrosis (MF), and chronic lymphocytic leukemia (CLL).

### **7.2 Secondary Objectives**

Part A and B:

- To evaluate the pharmacokinetic (PK) profile of ASN002 after single and multiple doses.

### **7.3 Exploratory/Pharmacodynamic Objectives**

Parts A and B:

- To evaluate the effects of ASN002 on Phospho-STAT3, Phospho-S6, Phospho-SYK 525/526, Phospho-ERK, and a panel of markers of inflammation (**Appendix C**)
- Evaluate the response to therapy based on DLBCL molecular subtype [germinal center B-cell like (GCB) or activated B-cell (ACB)].
- To evaluate the effects of ASN002 on JAK (V617F) mutant allele burden in subjects with MF.
- To evaluate the effects of ASN002 on BCL2, and chromosome 17p.

## **8 INVESTIGATIONAL PLAN**

### **8.1 Study Design**

This study will be performed at approximately 3 to 15 study centers located in the United States and Latin America.

The study is an open-label, non-randomized, uncontrolled, multicenter, dose escalation, cohort expansion and extension study with single and multiple-dose PK in subjects with relapsed/refractory lymphomas, MF, CLL, and advanced/metastatic solid tumors for which no standard therapy exists. The study will be conducted in 2 parts:

- Part A: Evaluation of the safety and tolerability of escalating multiple doses of ASN002;
- Part B: Cohort expansion of 6 identified disease-specific cohorts (DLBCL, MCL, FL, PTCL, MF and CLL) from Part A to further evaluate the safety, tolerability and antitumor activity of multiple doses of ASN002.

Parts A will be a “3+3” dose escalation scheme beginning with dose level 1 at a dose of 10 mg every 12 hours. Subjects will receive a single dose of ASN002 on Day 1, followed by every 12 or 24 hours, as assigned, dosing beginning on Day 3. The dose of ASN002 will be escalated to identify DLTs, and the MTD. If an MTD is not identified by the last scheduled cohort, dose escalation will continue in less than or equal to 50% increments until the MTD is identified. If supported by the PK profile, transition to once daily dosing may be considered. The starting dose of the once daily (qd) dosing cohorts will not exceed the total daily dose of the highest twice daily dose that is considered safe and well tolerated. Daily dosing cohorts may include doses beginning at 60 mg QD. Additional dose escalation may be performed for the qd dose cohorts, if the MTD is not identified by the 100 mg qd dose.

[figure not shown]
The study design includes a screening period (up to 28 days), and a DLT observation period of 28 days (Cycle 1). A subject with no DLTs during Cycle 1 will have the opportunity to continue to receive ASN002, at the discretion of the investigator. Subjects that are not able to complete Cycle 1 for reasons other than DLT will be replaced. Subjects participating in Parts B who discontinue from the study due to non-compliance or protocol violations may be replaced at the discretion of the Sponsor. Subjects may receive treatment with ASN002 in the absence of intolerable toxicity or disease progression for up to 12 months. If the subject is not a candidate for or chooses not to participate in additional treatment cycles, an end of treatment visit will be performed. A follow-up visit will be performed at least 30 days after the last dose of study medication.

In Part A of the study, after the Safety Review Committee (SRC) has met and agreed to dose escalation, up to 3 additional subjects may be allowed in a lower cohort to gather additional PK, PD and safety data. The inclusion of these subjects will be based on agreement with members of the SRC and the Sponsor.

Part B will be an expansion of the MTD cohort into 6 disease-specific groups to evaluate preliminary clinical anti-tumor activity. Each cohort will contain up to 14 subjects with DLBCL,

MCL, FL, PTCL, MF, and CLL. Subjects may receive treatment with ASN002 in the absence of intolerable toxicity or disease progression for up to 12 months.

The study design is illustrated in **Figure A**. The Schedule of Assessments for all parts of the study is located in **Table 1** and **Table 2**.

**Figure A: Study Schema**

## 8.2 Number of Subjects

Approximately 148 evaluable subjects will be enrolled in the study

Part A: Approximately 64 subjects which includes 40 subjects currently enrolled and an additional 24 subjects in cohorts dosed in fasted or fed states.

Part B: Eighty-four subjects in 6 groups of 14 each. The 6 groups are patients diagnosed with relapsed/refractory DLBCL, MCL, FL, PTCL, MF, and CLL.

Assuming a 10% early termination rate, the total number of subjects is approximately 163.

## 8.3 Selection of Doses

### 8.3.1 Part A (Dose Escalation)

Dose escalation will commence with dose level 1 (10 mg every 12 hours). Subsequent planned dose levels in Part A include: 20, 30, 40, 50, 75 and 100 mg administered every 12 hours or, 80, 120, and 150 mg every 24 hours. These planned dose levels may be modified based on data obtained throughout the course of study conduct. If an MTD is not identified after completion of the highest scheduled dosing cohort (either bid or qd) dose escalation may continue in

increments of  $\leq 50\%$  until the MTD is identified. The doses for twice daily and the single daily doses are found in **Table 6**.

The PK of ASN002 may be evaluated when administered with food. Up to 6 subjects per dose cohort may receive ASN002 after consuming a light meal. Subjects receiving ASN002 with food will receive no more than 75% of the highest dose that is deemed safe and well tolerated.

**Table 6: Twice Daily and Once Daily Dosing Cohorts**

Twice Daily Dose Cohorts		Single Daily Dose Cohorts	
1	10 mg	N/A	
2	20 mg	N/A	
3	30 mg	N/A	
4	40 mg	4a a	80 mg
5 a	50 mg	5a a	120 mg
6 a	75 mg	6a a	150 mg
7 a	100 mg		

a Cohorts may be administered ASN002 with and/or without food.  
Dose escalation may continue in increments of  $\leq 50\%$  until the MTD is identified

### 8.3.2 Part B (Cohort Expansion)

Based on the safety and tolerability data from Part A, the initial dose for Part B is 75 mg BID for subjects with hematologic malignancies, including lymphoma, CLL and MF. Dose adjustments for individual subjects may be made based on observed toxicity per Section 8.3.3.

